**Transcranial Photobiomodulation for
reducing autism symptoms in
children.**

October 1, 2020

PROTOCOL TITLE:

Transcranial photobiomodulation for reducing autism symptoms in children.

PRINCIPAL INVESTIGATOR:

Name	[name]
Department	N/A
Phone Number	

CO-INVESTIGATORS:

Name	[name]
Department	N/A
[contact]

Name	[name], CFA, Esq.
Department	N/A
[contact]

1.0 Purpose of the study:

The purpose of this 8-week open label feasibility study is to assess the tolerability, safety and efficacy of Transcranial LED Therapy for language learning and reducing symptoms of autism in children.

The investigators propose to enroll up to 30 participants of both genders ages 24 months to 6 years who have been previously diagnosed with moderate to severe ASD by licensed professionals according to the Diagnostic and Statistical Manual of Mental Disorders, Fifth Edition (DSM-5) criteria for Autism Spectrum Disorder (ASD).

The hypothesis to be tested is that exposure to photobiomodulation and speech parsing program will reduce children's symptoms of autism, such as delays in language production and comprehension, anxiety, tantrums, limited eye-contact and improve responsiveness.

2.0 Background / Literature Review / Rationale for the study:

2.1 Background Science of Photobiomodulation and Rationale:

There are several studies that suggest that mitochondrial energy disturbance is an underlying mechanism of autism, for at least some of the children. Specifically, Weisman, Kelley, Bauman, Cohen, Murray, Mitchell and Kern (2008) looked at the medical records of 25 children diagnosed with autism and found that "Levels of blood lactate, plasma alanine, and serum ALT and/or AST were increased at least once in 76%, 36%, and 52% of patients, respectively". Furthermore, 2 out of those 25 people had rare mtDNA mutations. The authors concluded that at least for a subset of ASD children, mitochondrial disturbances in energy production could be the underlying mechanism. Furthermore, Giulilvi, Zhang, Omanska-Klusek, Ross-Intra, Hertz-Picciotto, Tasson and Pessach (2010), looked at biochemical markers of ASD kids (2-5yo), and concluded that ASD children are more likely to have Mitochondria dysfunction, mtDNA replication and mtDNA deletion than neurotypical ones.

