This is a private professional office, with a waiting room and a receptionist. There are several private rooms within the office.

The child will be led to a private room, which will have toys and books inside it. The caregiver and one of the researchers will be present in the room at all times.

[name]

This is a private professional office, with a waiting room and a receptionist. There are several private rooms within the office.

The child will be led to a private room, which will have toys and books inside it. The caregiver and one of the researchers will be present in the room at all times.

7.0 Procedures Involved:

7.1 Location: The study will use pre-test and post-test design. The entire study on the children will be done in the office. The weekly interview with the parent may be done either in office or by phone, as preferred by the parent.

7.2 Conditions: There are two conditions: placebo condition, and combined light and audio therapy treatment condition. The placebo control condition will listen to nursery rhymes. **The placebo control condition will wear the same device, however the lights are not going to be turned on. Otherwise, all experience for participants in control and experimental conditions will be identical.**

This study replicates and extends previous studies of photobiomodulation in children older than 5 years of age (Leisman et al, 2018).

7.3 Participants: The participants will be matched on age, gender and number of hours of therapy they receive independent from the study. The participants will be 24-71 month old children previously diagnosed with moderate or severe ASD. The experiment will use random assignment. We plan to use 30 participants (15 in each group). **We plan to screen about 40 participants (or fewer) to recruit the 30 participants for this study.**

7.4 Random Assignment: Random assignment will be achieved by using random number generator programs frequently used in research (such as random.org). Each participant is assigned a number. The list of 30 numbers is entered into the program, which creates a random sequence of 30 participants. Here is an example of the beginning of such list generated for 30 participants

1 – 23

2 – 25

1 – 12

2 – 15

1 – 21

2 – 5

1 – 19

2 - 9

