	
interaction is extremely unlikely. The positive interaction (e.g., children becoming more responsive to ABA therapy) will also be monitored and recorded in parental diaries. The children should be able to receive their regular behavioral therapies while being enrolled in this study.

There may be risks that we do not know about yet. Exposure to LED lights is not known to have any negative side effects.
	
 • When the child will wear the headband, the child will be exposed to LED lights. The lights will be both red and near infra red. The lights will range in frequency

	
from 660 MHz to 850 MHz.
 
 • After years of study, there are no known negative side effects of photobiomodulation. • Throughout the study, we'll tell parents if we learn anything that might affect their decision to let their child participate.

Some participants may have to be withdrawn from the study
	
 • If the child is not able to attend all the required sessions and the caregiver is not able to reschedule a cancelled session within a 3 day window, then the child will have to be withdrawn from the study. • If the child becomes aggressive or self-injurious

	
during the session, then the child will have to be withdrawn from the study.
 
 • In that event, only the data that has been collected up to the date of withdrawal will be kept. • All identifying information will not be shared and all reports will be aggregated. • We will ask the child's parents for permission to contact them in the future with follow up questions regarding the child's behavior.

Furthermore, the study will be under oversight of [name], who is a board-certified pediatric psychiatrist with more than 10 years of experience working with children with ASD
	

14.0 Provisions to Protect the Privacy and Confidentiality of Participants and the Research Data:

Participants will be only interacting with [name] or [name], Esq. Participants and their parents will be tested individually, in a quiet room, and their confidentiality will be protected, as they won't be interacting with each other or with anybody else outside of the researchers.

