The participants will be explained that they can refuse to answer any question. They can also refuse to participate in the study at any time. We do not anticipate uncomfortable questions, however, we will assure the participants that their level of comfort is of utmost importance, and we will explain to them that there is no penalty involved for their refusal to answer any specific question.

Only [name] and [name] will be able to access individual information. The participants will be immediately assigned Study ID number and only STUDY ID will be used for data analysis and reporting. Only aggregated data will be used for further reporting to the scientific community or to the business community. Individual data will be reported for illustrative purposes only with STUDY ID (not identifying personal information).

The following information will be included as data: Signed consent form (immediately scanned and stored in a cloud). Pre and Post-test Cars2 scores (with STUDY ID assigned). Weekly interview data (with STUDY ID assigned).

Identifying information will include Name and Age, Gender and number of therapy hours of the participant, Name and phone number of the parent. Children's age, gender and number of therapy hours will be used for matching purposes (for assigning to the control or treatment condition). Neither names of the participants nor names and phone numbers of their parents will be used for data analysis or reporting. Their names and phone numbers will be stored separately, in encrypted (password protected) file, in a secure cloud. Secure clouds as well as encryption and password protection will be used to protect identifying information.

The raw research data will be stored for 6 years. The identifying parental information will be kept for a year, for potential follow up interviews. The consent form will include their permission to keep identifying data for a year.

Although we do not plan to re-contact the participants after the study is complete, a follow up interview in 6 months or a year could be useful to assess the sustainability of the benefits of photobiomodulation. In this case, we will be applying for a separate IRB (minimal risks) to conduct the follow up interview. Presently, we do not plan to do it (although we recognize that it could potentially be useful for research purposes).

The data will be stored in encrypted, password protected files in a secure cloud.

15.0 Data Monitoring Plan to Ensure the Safety of Participants:

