We will conduct weekly interviews with the parents, asking them questions about child's behavior and functioning to collect both safety and efficacy data. The interviews will be conducted either by telephone or in person (per parental choice). Please attached interview protocol. [name], a licensed clinical psychologist will review the data. The detailed qualitative data will be collected. No statistical analysis is necessary.

If a participant shows sudden developmental regress, we will recommend immediate neurological evaluation and his/her participation will be discontinued (unless this participant has been manifesting regress prior the start of the study). If two participants suddenly manifests signs of regress (not anticipated, not seen before in prior photobiomodulation studies), we will immediately discontinue the study.

16.0 Data, and if applicable, Specimen Banking:

The raw research data will be stored for 6 years. The identifying parental information will be kept for a year, for potential follow up interviews. The consent form will include their permission to keep identifying data for a year.

Although we do not plan to re-contact the participants after the study is complete, a follow up interview in 6 months or a year could be useful to assess the sustainability of the benefits of photobiomodulation. In this case, we will be applying for a separate IRB (minimal risks) to conduct the follow up interview. Presently, we do not plan to do it (although we recognize that it could potentially be useful for research purposes).

The data will be stored in encrypted, password protected files in a secure cloud.

17.0 Data Sharing:

Only aggregated data will be shared with scientific community (via publications). Only aggregated data will be shared with potential investors. If individual data (e.g., from an interview) is shared for illustrative purposes, identifying information will NOT be shared (STUDY ID will be assigned to each participant).

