## Data Collection and Statistical Analysis

### Primary Analyses

The last author, a licensed psychologist experienced in the use of CARS in clinical practice, conducted blinded Before and After CARS ratings for all participants. The final CARS evaluations were performed immediately after the final treatment session. CARS scores were analyzed using the independent sample t-test. We compared the differences from the baseline between both groups, calculating both the average difference and 95% CI within each group and between groups.

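### Children removed for suspected harm have no scheduled, defined safety follow-up: the event is recorded, its outcome is not

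*Protocol*

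**What the plan says.** - **Purpose.** Protocol 1.0 sets out to "assess the tolerability, safety and efficacy of Transcranial LED Therapy" over 8 weeks.
- **Safety data during treatment.** Parents keep a daily diary (7.7). They are also interviewed weekly, "asking them questions about child's behavior and functioning to collect both safety and efficacy data" (15.0). A psychologist reviews the data, and 15.0 sees no need for statistical analysis.
- **Sudden regress.** Under 15.0, "we will recommend immediate neurological evaluation and his/her participation will be discontinued", except where the child was already regressing before the study. A second such child stops the study.
- **Aggression or self-injury in a session.** Under 13.0 the child is withdrawn and "only the data that has been collected up to the date of withdrawal will be kept". The same list says parents will be asked for permission to be contacted later about the child's behaviour.
- **Voluntary withdrawal.** The withdrawal text under 8.0 ends all data collection after full withdrawal. After withdrawal from the intervention only, the team may ask to collect follow-up data on behaviour.
- **Replacement.** Under 5.0 the team tries to replace children who drop out.
- **After completion.** 14.0 and 16.0 state that "we do not plan to re-contact the participants after the study is complete". An interview at 6 or 12 months is mentioned only to see whether benefit lasts. Parents' identifying details are kept for a year.
- **Last rating.** The SAP (Primary Analyses) says: "The final CARS evaluations were performed immediately after the final treatment session". It describes post-treatment ratings for those who completed, 16 active and 14 sham.

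**The concern.** The removal rules select the few children in whom the device may have done harm, and the plan does not schedule any way of learning what became of them. For regress, the protocol goes as far as recommending a specialist evaluation, then ends participation without a step that brings the result back. For aggression and self-injury, one line closes the record at withdrawal and a nearby line opens the door to later contact, with nothing to say which governs safety information.

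Replacement adds to this. A removed child can be succeeded by another, and the reported ratings cover completers. Unless exits are reported separately, the removed child need not appear in the results at all. The study could then say that an event occurred, but not whether it was brief, lasting or unrelated to the device. In a feasibility study with safety among its first-named purposes, that is information a later trial would need.

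**Working it through.** The documents give no safety sample size, event rate or follow-up length, so there is no figure to reproduce. The check is a comparison of the texts, followed by a calculation of how much one case weighs.

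**1. What is recorded, by route of exit**

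| Route | Up to exit | After exit |
|---|---|---|
| Sudden regress (15.0) | Diary, weekly interview, the event itself | Evaluation recommended; no step to obtain or file its result; no contact scheduled |
| Aggression or self-injury in session (13.0) | The same, including the event | Record closed at withdrawal; permission for behaviour questions to be sought, with no date, form or safety content |
| Withdrawal from intervention only (8.0) | The same | Permission for behaviour follow-up may be sought |
| Full withdrawal (8.0) | The same | None, by the family's choice |

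The data cut-off in 13.0 attaches to missed sessions and to aggression or self-injury. The regress rule in 15.0 has no cut-off of its own; what it lacks is any collection step. The list of study data in 14.0 has no entry for an evaluation result. That is only supporting evidence, because the list also omits the diaries and the EEG.

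**2. How much one child weighs**

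Input: 15 planned active children (7.3). One child is 1/15 = 6.7% of the arm. Exact (Clopper-Pearson) two-sided 95% limits:

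- 0 of 15: upper limit = 1 − 0.025^(1/15) = 1 − 0.782 = 21.8%.
- 1 of 15: lower limit = 1 − 0.975^(1/15) = 0.2%. The upper limit solves (1 − p)^15 + 15p(1 − p)^14 = 0.025, giving p = 31.9%.
- With the 16 active children in the SAP, the upper limits are 20.6% (0 of 16) and 30.2% (1 of 16).

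If k of 15 leave with unknown outcome and the others have no lasting harm, the observed proportion with lasting harm lies between 0 and k/15:

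| k | Highest possible proportion | 95% upper limit if all k were lasting harm |
|---|---|---|
| 1 | 6.7% | 31.9% |
| 2 | 13.3% | 40.5% |
| 3 | 20.0% | 48.1% |

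**3. Would a case be expected?**

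The documents give no rate, so this is an assumed range. The chance of at least one event among 15 children is 1 − (1 − p)^15: 26% at p = 2%, 54% at 5% and 79% at 10%.

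**4. What the limits measure**

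A child removed for regress is already a recorded event, so the count of triggering events is 1 of 15 with or without follow-up. What stays undetermined is the count of lasting or attributable harm, which could be 0 or 1 of 15. Follow-up would settle which count applies. It would not narrow either interval.

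**The case against.** The case on the other side is substantial, and much of it stands.

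- **Observation does not simply end at exit.** A reader might infer that it does. The documents do not support that: 13.0 commits the team to asking for permission for later contact, the withdrawal text allows it after partial withdrawal, and contact details are kept for a year. In this protocol, questions about behaviour are the safety instrument. The defect is that this contact has no schedule or defined content and sits beside a contrary data rule.
- **Harm would not go unseen.** Diaries and weekly interviews cover the treatment period, the triggering event falls within retained data, and 13.0 provides oversight by a pediatric psychiatrist. The gap is limited to what follows the event.
- **Completers.** A reader might infer that they have no safety observation at all after the last session. The SAP sentence times the CARS rating only. No text dates the last weekly interview, which may be by phone, and the point at which the study counts as complete is not defined. Nor do the headache and tiredness named in 9.0 make the case, since that section confines them to first-time users.
- **Share of exposure left unobserved.** Eight weeks at two sessions a week gives 16 sessions, but 7.6 places the post-treatment EEG at Session 8. A figure such as 1 in 16 is therefore unsafe and is not used.
- **The limits of 22% and 32% reflect 15 children.** This is correct, and they are presented above only as the weight of one case.
- **Unseen material.** Part of the SAP, the consent pages and the interview script were not available. Nothing here relies on silence in those places, and a provision there could close part of the gap.

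None of this supplies the result of the recommended evaluation, or says which of the two lines in 13.0 governs safety information.

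**Conclusion.** The concern holds in a limited form. For children removed for regress, aggression or self-injury, the plan records the event but does not secure its severity, persistence, resolution or attribution. The two statements in 13.0 on data and contact after withdrawal must be reconciled. With about 15 treated children, one unresolved case leaves open whether lasting harm is 0% or 6.7% of the arm, with upper limits of 22% or 32%. The plan itself treats a second regress as reason to stop the study, so single cases matter.

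This assumes that at least one child is removed for such a reason, which the available text neither confirms nor excludes, and that the unavailable attachments do not already provide for it. It does not support the stronger statement that the study lacks data wherever harm would show. It has no bearing on the CARS comparison. The point about completers is weak and is left as an option. The change for removed children should be made: it is cheap, and following the rules as written would leave these outcomes unresolved.

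**What to change.** 1. In 13.0, state that the withdrawal cut-off does not apply to safety information collected with parental permission. This also reconciles the two lines there.
2. In 13.0 and 15.0, ask at consent for permission to (a) receive the result of the evaluation that 15.0 already recommends and (b) continue the existing weekly phone interview to the planned 8-week point for any child removed for regress, aggression or self-injury. File both under the Study ID. Full withdrawal, as set out under 8.0, still ends all collection.
3. Add one open safety question to those interviews. The topics listed in 7.7 cover language, behaviour, eating and sleep, and do not include physical complaints such as headache.
4. Report all exits and their outcomes by arm, including children who were replaced.
5. Optionally, place the last weekly interview for completers a few days after the final session.

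**Cost.** A consent sentence, a protocol amendment and slightly more burden on parents. Weekly calls to week 8 come to at most 8 − 1 = 7 extra calls for a child removed in week 1, and fewer for later exits. The option for completers moves an interview rather than adding one. No treatment or stopping rule changes.

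If conduct is already over, as the SAP's past tense suggests, item 4 can still be done. The report should then say which removed children had no recorded outcome and that no defined safety follow-up was scheduled for them.

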## Data Collection and Statistical Analysis

### Primary Analyses

The last author, a licensed psychologist experienced in the use of CARS in clinical practice, conducted blinded Before and After CARS ratings for all participants. The final CARS evaluations were performed immediately after the final treatment session. CARS scores were analyzed using the independent sample t-test. We compared the differences from the baseline between both groups, calculating both the average difference and 95% CI within each group and between groups.

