3.0 Safety of the Device

We are asking the Board to make a non-significant risk determination.

The device is not approved or marketed.

The device does not pose a risk to participants under 21 CFR 812.3(m).

This investigational device is not:

- Intended as an implant and presents a potential for serious risk to the health, safety or welfare of a participant;
- Purported or represented to be for use supporting or sustaining human life and presents a potential for serious risk to the health, safety or welfare of a participant
- For a use of substantial importance in diagnosing, curing, mitigating or treating disease or otherwise preventing impairment of human health and presents a potential for serious risk to the health, safety or welfare of a participant or
- Otherwise presents a potential for serious risk to the health, safety or welfare of a participant.

Please see Response to January 15 New England IRB Letter, specifically Responses to Questions 5 and 6, for a full explanation of the device safety and comparison to other predicate devices. .

4.0 Inclusion and Exclusion Criteria:

Inclusion Criteria:

1. Male or female participants between 2 years and 6 years of age (inclusive), of all races.
2. Previously diagnosed with moderate or severe ASD by a licensed professional.

3. Participants may be receiving any behavioral intervention therapy (e.g., ABA, Floor Time) during the course of the treatment. The final statistical analysis will control for the participants receiving behavioral therapies in control and experimental conditions. We expect the majority of the participants in both control and experimental conditions to be receiving behavioral therapies. There is no known interactions or complications of tPBM with behavioral therapy.

4. Parents of participants must understand the nature of the study.
5. Parents of participants must sign an IRB- approved informed consent form before initiation of any study procedures.
6. Parents of participants must have a level of understanding sufficient to communicate with the investigator and study coordinator, and to cooperate with all tests and examinations required by the protocol.
7. Participant child experiencing a major psychiatric disorder will be allowed to participate in the study provided they do not meet any exclusionary criteria.
8. The participant child is willing to participate in this study.

Exclusion Criteria:

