Once the program generates the random sequence of 30 participants (in the example above, the sequence goes 23, 25, 12, 15, etc), we will simply alternate the assignment to treatment and control conditions. For example, in the example above, participant number 23 is assigned to the treatment condition (1), and participant number 25 is assigned to the control condition (2). Because the sequence of the participants is randomized, the assignment to conditions is random.

7.5 Treatment: The treatment will take place twice a week for up to 30 minutes at a time.

During the study, while participants will be wearing the photobiomodulation device, they will be listening to the audio program, and they may be playing with their parent or the experimenter, using the toys of their choice (out of the many available in the experimenter’s office). The caregivers will be present during the experiment at all times. When the child and the parent arrive, they will be welcomed to the office, and introduced to the toys.

The child will be encouraged to play with toys and interact with the parent (or the experimenter). The children in the experimental condition will be asked to wear the device for no longer than 15 minutes. The children in the controlled condition will play for 30 minutes and wear the same device, without turning it on (the device won’t be turned on at that time). The total time in the office will be about 30 minutes (including playing).

If the child becomes uncomfortable, the parents will be able to leave the experiment without any punishment. No coercion or deception is involved in this study.

7.6 Pre and Post-Testing: CARS2 will be used for pretest and post-test. Please see attached a sample CARS 2 test. CARS 2 scores will be compared for analyses. **In addition, EEG will be collected from the participants in both Control and Experimental conditions pre and post -treatment (before Starting treatment in session 1 and in the end of treatment of Session 8). Mobile FDA approved EEG device Brain Scientific will be used to collect children's pre and post test EEG. There is no known danger of EEG collecting. In this study it will be using for measuring the efficacy treatment only.**

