7.7 On-going Data Collection: Parents will be asked to keep a daily diary of the child's behavior, specifically – words spoken, comprehension of instructions, eye contact, his sleep pattern, number of tantrums, anxiety, social interaction and eating. Qualitative data will be collected through short weekly interviews with the parents. These interviews can take place either in [name] office during the child's treatment or by phone. During those weekly interviews, the parents will be asked questions about their children's responsiveness to language, number of words they can produce, eye-contact, anxiety, frequency of tantrums, eating, and difficulties falling asleep and sleeping through the night. Please see attached proposed script for the weekly call. The qualitative data will be used to further inform and supplement quantitative data (total CARS 2 scores).

The study will collect qualitative and quantitative data. The quantitative data will be the total CARS2 scores of the participants of both Control and Treatment groups, obtained before and after the study is done. Mixed Design Analysis of Variance will be used to analyze quantitative data. **In addition, we will collect Before and After Prefrontal cortex EEG from the control and experimental treatment groups to measure electrophysiological changes in Prefrontal cortex. after treatment. EEG data will be analyzed (using Time-Frequency analysis), and after baseline normalization, the data will be used in aggregate to compare conditions numerically. The between group comparison before the treatment will be conducted using between subject T-test for each brainwave . The between group comparison will be conducted after treatment for each brain wave using between subject t-test. In addition, for the treatment condition only Before and After comparison will be conducted, using within subject t-test.** In addition, we will obtain qualitative data from weekly parental interviews, during which we will ask participants' parents about their children's behavior (see attached protocol). Qualitative data will be used for information purposes and will supplement quantitative data.

7.8 Blinding of the Researcher: [name] (the PI) will not be present in the room when the child is receiving the treatment. She will not be aware what group each particular participant has been placed in. [name] will be conducting the pre and post-testing interviews, as well as the on-going weekly interviews with the parents.

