### Outcomes

#### Baseline Data

At the beginning of the trial, an initial evaluation was performed to assess the severity of ASD in participants using the CARS score. **Table 1** displays the mean, median, and range of the participant scores. Most participants had moderate to severe ASD, with a CARS score higher than 35. There were no significant differences in age, gender, ethnicity, language status, treatment status, or CARS scores between the Active and Sham groups.

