#### Primary Outcome

Every participant who completed the trial was evaluated with CARS post-treatment. There were no missing CARS posttreatment evaluations. In the Active group, the before treatment CARS scores had a mean score value of 43.5 ( $n = 16$ ) with a standard deviation (SD) of 5.7, the after-treatment scores had a mean score of 33.7 with an SD of 5.0. In the Sham group, the before treatment CARS scores had a mean score value of 40.6 ( $n = 14$ ) with SD of 7.2, the after-treatment scores had a mean score of 38.0 with SD of 8.4. **Table 3** shows the mean (M) and SD of the CARS scores for the Active and Sham groups before and after treatment. The difference in the change in CARS between the two groups was 7.23 (95% CI 2.357 to 12.107,  $p=0.01$ ).

In addition to analyzing the changes in CARS scores based on averages, we also conducted respondents-based analyses, quantifying the number of participants in Active and Sham groups, whose change in CARS was greater than 4.5 points (as it has been suggested by Jurek et al 2022 to be the minimal clinically important difference). The result was significant  $\chi^2=8.48$ ,  $p=.004$ . By the end of the trial, 87% of the participants in the Active group (14) had achieved an equal or greater than 4.5-point reduction in CARS scores, only 35% of the participants of Sham group (5) achieved an equal or greater than 4.5-point reduction in CARS scores. The number of subjects that achieved this minimal clinically important difference in the Active group was statistically significantly higher compared to the Sham group. Therefore, the treatment was considered to have clinically meaningful efficacy.

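### The primary t-test on CARS change does not adjust for baseline CARS, although Active started 2.9 points worse; adjustment lowers the effect from 7.23 to about 5.9 points

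*SAP*

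**What the plan says.** SAP, Primary Analyses: "CARS scores were analyzed using the independent sample t-test. We compared the differences from the baseline between both groups". No covariate is named there, and no baseline-adjusted analysis appears in the SAP text available for review, from which one part was removed.

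SAP, Primary Outcome, gives these CARS figures:

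- Active (n = 16): mean 43.5 (SD 5.7) before and 33.7 (SD 5.0) after.
- Sham (n = 14): "In the Sham group, the before treatment CARS scores had a mean score value of 40.6" (SD 7.2), and 38.0 (SD 8.4) after.
- Result: "The difference in the change in CARS between the two groups was 7.23 (95% CI 2.357 to 12.107", with p = 0.01.

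SAP, Baseline Data: "There were no significant differences in age, gender, ethnicity, language status, treatment status, or CARS scores between the Active and Sham groups".

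The protocol names a different procedure in section 7.7: "Mixed Design Analysis of Variance will be used to analyze quantitative data". On concurrent therapy, section 4.0 (inclusion criterion 3) states: "The final statistical analysis will control for the participants receiving behavioral therapies in control and experimental conditions". Section 7.3 adds: "The participants will be matched on age, gender and number of hours of therapy they receive independent from the study", and section 14.0 repeats that plan. The assignment steps in section 7.4 take a random sequence of participant numbers, after which "we will simply alternate the assignment to treatment and control conditions".

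**The concern.** A comparison of raw changes is the right correction for a baseline gap only if each extra point at baseline carries over in full to the post-treatment score. If the carry-over is smaller, the arm that starts worse is expected to fall further whatever the treatment does. Here that arm is Active, so the reported effect would be too large for the imbalance that occurred.

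The protocol's mixed-design ANOVA does not change this. With two time points, its group-by-time test is the same t-test on change.

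The finding of no significant baseline difference in CARS does not settle it either. The SAP does not offer it as a reason for leaving out adjustment. With 30 children, what moves the estimate is the size of the gap, not its p-value.

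At stake are the headline effect and its lower confidence limit. The protocol calls this a feasibility study, so the estimate may be carried into the sample size of a later trial.

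A second, smaller gap is that the protocol promises control for behavioral therapies and the t-test contains none. Matching on therapy hours is planned, but no step of the described assignment uses those hours.

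**Working it through.** All inputs are the summary figures in SAP, Primary Outcome.

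**1. Reproduce the reported effect.** The rounded means give (43.5 − 33.7) − (40.6 − 38.0) = 9.8 − 2.6 = 7.20. The CI midpoint is 7.232. The stated 7.23 is reproduced.

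**2. Standard error behind the CI** (equal-variance t, 28 df). SE = (12.107 − 2.357)/2 ÷ 2.048 = 4.875/2.048 = 2.380. Then t = 7.232/2.380 = 3.04 and p = 0.005, which rounds to the reported 0.01.

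**3. Variance of the change.** SD = 2.380/√(1/16 + 1/14) = 6.50; variance 42.29.

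**4. Pooled within-arm variances.**
- Before: (15 × 5.7² + 13 × 7.2²)/28 = 41.47 (SD 6.44)
- After: (15 × 5.0² + 13 × 8.4²)/28 = 46.15 (SD 6.79)

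**5. Slope of post on pre.** Covariance = (41.47 + 46.15 − 42.29)/2 = 22.67. Slope = 22.67/41.47 = 0.547; correlation 0.518. The residual variance is (46.15 − 0.547 × 22.67) × 28/27, so the residual SD is 5.92 (27 df). The slope's SE = 5.92/√(28 × 41.47) = 0.174, which gives a 95% CI of 0.19 to 0.90. Against a slope of 1, t = (1 − 0.547)/0.174, about 2.61, p = 0.015.

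**6. Baseline gap.** 43.5 − 40.6 = 2.9 points, or 2.9/6.44 = 0.45 SD (t = 1.23, p = 0.23).

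**7. Adjusted effect.** (38.0 − 33.7) + 0.547 × 2.9 = 4.3 + 1.59 = 5.89. SE = 5.92 × √(1/16 + 1/14 + 2.9²/(28 × 41.47)) = 2.22. The 95% CI is 1.32 to 10.45, p = 0.013.

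**8. Excess of the change score.** 2.9 × (1 − 0.547) = 1.31; measured against 7.23 it is 1.34. Over the slope's CI it runs from 2.9 × (1 − 0.90) to 2.9 × (1 − 0.19), or 0.28 to 2.35 with unrounded limits. The adjusted effect then runs from 6.9 down to 4.9.

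| Analysis | Difference | 95% CI | p |
|---|---|---|---|
| Post-treatment scores only (slope 0) | 4.3 | −0.8 to 9.4 | 0.095 |
| Baseline-adjusted (slope 0.547) | 5.9 | 1.3 to 10.4 | 0.013 |
| Change score (slope 1), as reported | 7.23 | 2.36 to 12.11 | 0.005 from the CI |

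**9. Sensitivity.**
- Rounding of the inputs: 5.85 to 5.98.
- CI taken from a Welch test: about 5.8 to 6.2.
- p taken as exactly 0.010 instead of the CI: SE 2.62, slope 0.44, adjusted effect 5.6 (0.7 to 10.4, p = 0.026).
- Arm-specific slopes: at the overall mean baseline of (16 × 43.5 + 14 × 40.6)/30 = 42.15, the effect is 4.3 + 1.547 × Sham slope + 1.353 × Active slope. Varying the Active correlation from 0 to 0.9 requires a Sham correlation from 0.81 to 0.32 to keep the reported CI. The effect is then 5.8 to 5.9.

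**The case against.** The strongest reply is that the analysis contains no error. Under randomisation the change-score estimator is unbiased, the contrast equals the protocol's group-by-time test, and an ANCOVA added now would be post hoc. No conclusion turns on it: 7.23 and 5.89 both exceed the 4.5-point threshold that the SAP uses, both lower limits fall below it, and the gain in SE (2.22 against 2.38) is small. All of this is correct. It bears on how the adjusted result is presented, and does not show that 7.23 is the best estimate given the imbalance that occurred.

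A sharper point concerns the pooled slope. Regression to the mean is about untreated children, so the Sham slope matters most. The post-treatment SDs of 5.0 and 8.4 make a common slope doubtful. In the arm-specific scenarios above, the Sham slope runs from 0.94 to 0.37 and its 95% CI includes 1 throughout (p from 0.78 to 0.07). At the Active mean baseline the effect is 4.3 + 2.9 × Sham slope, or 5.4 to 7.0. The stable 5.8 to 5.9 at the overall mean arises partly because the two slopes have nearly equal weights there. This stands: the 1.3 points depend on the model. Even so, the effect stays below 7.20 in every scenario.

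On therapies, the SAP reports no significant difference in treatment status, and the removed part of the SAP might describe covariates. Neither alters the fact that the primary analysis, as described, is a t-test without them.

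**Conclusion.** The concern holds and should be fixed. Given the observed 2.9-point imbalance, the baseline-adjusted difference is about 5.9 points rather than 7.23. That is a reduction of about 1.3 points or roughly a fifth (1.34/7.23 = 19%), and the lower confidence limit falls from 2.4 to 1.3. This describes the estimate in this trial; it is not a general bias of change scores. The result still favours Active and remains significant at 0.05.

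The figure rests on a common linear slope, an equal-variance t-test behind the published CI, and back-calculation from summary data. The individual data would give the exact value.

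The missing control for behavioral therapies is a separate departure from protocol section 4.0. It contributes nothing to the 1.3 points.

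**What to change.** - Fit an ANCOVA of post-treatment CARS on arm with baseline CARS as covariate, using the individual data and robust standard errors because the post-treatment SDs differ.
- Report the adjusted difference and its 95% CI prominently beside the change-score contrast, which stays as the planned comparison.
- State that the ANCOVA was not prespecified and was added after results were known.
- Do not rely on non-significant baseline tests as evidence that adjustment is unnecessary.
- Separately, add the collected number of therapy hours as a second covariate, or state that this control was not done and why.

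The cost is one regression on data already held, one degree of freedom per covariate, and a sentence of disclosure. The reported effect becomes somewhat smaller.
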